1. LIST OF ABBREVIATIONS

VT	ventricular tachycardia
PVC	premature ventricular contraction
HR	heart rate
LV	left ventricle
RV	right ventricle
RVOT	right ventricular outflow tract
RF	radiofrequency current
EAM	electroanatomical mapping
EGM	electrogram
TOE	transesophageal echocardiography
TTE	transthoracic echocardiography
ECG	electrocardiogram
CT	computer tomography
F/U	follow-up
EP	electrophysiology
QoL	quality of life
PI	principal investigator
CMR	cardiac magnetic resonance imaging
VTK	visualization toolkit
RB&HFT	Royal Brompton and Harefield NHS Foundation Trust
AE	Adverse Event
AR	Adverse Reaction
ASR	Annual Safety Report
CI	Chief Investigator
CRF	Case Report Form
DMC	Data Monitoring Committee
GCP	Good Clinical Practice
HRA	Health Research Authority
ICF	Informed Consent Form
NHS R&D	National Health Service Research & Development
PI	Principal Investigator
PIS	Participant Information Sheet
REC	Research Ethics Committee
SAR	Serious Adverse Reaction
SAE	Serious Adverse Event

3. STUDY SYNOPSIS

Full study title:	VIVO™ non-invasive Time Assessment Protocol
Short study title:	VIVO™ mapping Protocol
Study R&D number:	VIVO-RBH01
Chief Investigator:	[name]
Medical condition/disease under investigation:	Patients undergoing PVC/VT Ablation with structurally normal hearts
Study duration:	9 months
Primary Objective:	
Safety:
 
 • Absence of acute adverse events due to the use of VIVO system during PVC/VT ablation • Safety endpoint of the entire mapping and ablation strategy 
Efficacy:
 
 • To assess the efficacy of VIVO to decrease procedure time as compared to standard of care ablation procedures.
Secondary Objective:	
 • To assess clinical outcome (suppression of reduction of PVCs burden/VT at 3-month F/U) • To assess economical outcome (cost reduction per case)
Study population:	
VIVO Cohort – 15 patients presenting for PVC/VT ablation with structurally normal heart
 
Control Cohort – Retrospective review of historical matched patients within the physician's database that had PVC/VT ablations with structurally normal hearts

Recruitment Target	15 patients
Recruitment Window (Months)	6 months
Methodology:	The study is a non-randomized, single-centre, study designed to evaluate the procedural efficacy of VIVO as compared to standard of care ablation procedures. Up to 15 patients will be enrolled.
Eligibility criteria:	
Inclusion criteria:
 
 1. Subjects who are at least 18 years or older 2. Subjects who are scheduled for PVC/VT ablation procedure 3. Subjects who have signed an IRB/EC approved Informed Consent Form and applicable subject privacy protection authorization per local law 4. Subjects will be selected without regard to gender or age (unless precluded by local regulatory requirements) 5. Subjects with or without cardiac structural disease
	
Exclusion criteria:
 
 1. Reversible causes of PVC/VT 2. Subjects with recent (within 3 months) acute coronary syndrome 3. Subjects who are contraindicated for CT or MRI (must be able to get one)

	
 4. Subject whose MRI or CT scan does not comply with the requirements of this protocol 5. Subjects who are contraindicated for an electrophysiology procedure and/or fluoroscopy: 6. INR > 3.5 7. Active infection 8. Pregnancy: Females of childbearing potential with a positive pregnancy test. 9. Existing mechanical heart valve 10. Subjects with structural cardiac disease
Study treatment: (i.e. dose and mode of the study drug administration if applicable): NA	

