6. STUDY DESIGN

6.1 OVERALL DESIGN

This is a prospective, single arm, observational and feasibility study, which will recruit 15 non-selected patients, with structurally normal heart, with a conventional indication for catheter ablation of PVCs/VT. The follow up will be of three months. The study will also include another retrospective cohort, including age & gender matched patients, without cardiac structural disease, with a conventional indication for catheter ablation of PVCs/VT from the last 5 years' database of the same operator. For this second retrospective cohort there will be no follow-up.

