13.3 DATA HANDLING AND ANALYSIS

- Excel software will be used for data entry.
- In order to ensure validity and quality of data we will use cross validation
- Data will be stored and backed up on 2 additional hard drives on two different sites in order to allow recovery of data in case of a disaster such as fire/flooding/ theft. The PI and their collaborators/co-workers will be responsible for data entry and quality of data collection. Analysis will be performed by the study investigators and reviewed independently of data entry by the statistical team.
- Every patient will receive a numerical patient identifier and all data that is transferred outside the primary hospital will exclusively be identified by this study number.
- The study database will be held at a server at the Royal Brompton Hospital.

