14. STATISTICAL DESIGN

This is a prospective, non-randomised, observational study which will recruit 15 non-selected patients with PVC/VT eligible for catheter ablation, without structural heart disease.

Procedural outcomes will be compared to age & gender matched procedures of the same operator from the last 5 years' database.

The statistical design was decided in collaboration with the study PIs and will be descriptive only.

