14.1 SAMPLE SIZE AND RECRUITMENT

This is a feasibility pilot study, which will test the feasibility of PVC/VT foci mapping with Vivo system and catheter ablation in unselected patients without structural heart disease, eligible for PVC/VT ablation. Therefore, no power calculation has been done and the number of patient recruited will be of 15 which are deemed sufficient by the CI and Co-PIs on a clinical basis.

The estimated recruitment period for the trial will be of 6 months. We estimate that this sample size is attainable in practice, as the number of PVC/VT ablation procedures per year performed within the Trust is around 100. We also included patients with previous PVC/VT ablation in order to maximise chances of recruitment. This pilot is performed with the intention to plan a prospective multi-operator/multicentre trial which is adequately powered. We will aim to compare the procedure parameters as well as the outcome of this trial to age & gender matched procedures of the same operators from the last 5 years' database.

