14.2 ENDPOINTS

14.2.1 Primary endpoints

Safety:

- Absence of acute adverse events due to the use of VIVO system during PVC/VT ablation
- Safety endpoint of the entire mapping and ablation strategy

Efficacy:

- To assess the efficacy of VIVO to decrease procedure time as compared to standard of care ablation procedures.

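### The plan has no rule, lock or masking for choosing historical controls whose procedure times already exist, so selection could inflate the apparent time saving

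*Combined protocol and SAP*

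**What the plan says.** The only primary efficacy endpoint in section 14.2.1 is "To assess the efficacy of VIVO to decrease procedure time as compared to standard of care ablation procedures". The comparator is described in the Study Synopsis as a "Retrospective review of historical matched patients" held in the physician's own database. Section 6.1 restricts it to "age & gender matched patients, without cardiac structural disease, with a conventional indication for catheter ablation of PVCs/VT", within a five-year window, and section 14 adds that "Procedural outcomes will be compared to age & gender matched procedures of the same operator". Section 14.3 repeats the comparison with one operator, while section 14.1 refers to operators in the plural.

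On who handles the data, section 13.3 says: "Analysis will be performed by the study investigators and reviewed independently of data entry by the statistical team". On the size of the source, the only figure is in section 14.1: "the number of PVC/VT ablation procedures per year performed within the Trust is around 100".

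The documents do not give the number of controls, the matching ratio, an age tolerance, a rule for choosing among several eligible matches, the person who selects, the date on which the list is fixed, or any masking of that person to procedure time. Section 14.6 (other statistical considerations) adds nothing.

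**The concern.** The VIVO cases are collected prospectively. The control cases are already complete, so the value of the primary endpoint exists for each of them when the control group is assembled. If more than one past case satisfies the matching criteria for a VIVO patient, somebody must decide which to use, and the plan leaves that decision open. A mild preference for long or memorable cases would raise the control mean and appear as a saving due to VIVO.

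This is separate from which variables are matched. Extra matching variables would shrink the pool, but would not settle who chooses among the cases that remain or what that person can see.

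More than one number is at stake. The time difference also bears on the cost-per-case endpoint (sections 5.2 and 14.2.2), and section 14.1 says the pilot is meant to lead to a powered multicentre trial. An inflated saving could carry into that trial's planning.

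**Working it through.** The plan states no power, effect size, SD or control number, so there is no figure of its own to reproduce. The check asks how large a spurious saving the open selection step allows when VIVO has no true effect.

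**Inputs from the documents**
- VIVO cohort: 15 (sections 6.1 and 14.1).
- Source: about 100 procedures a year across the Trust, over five years: 5 × 100 = about 500. This is an upper bound, because it covers all operators and is not limited to structurally normal hearts.

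**Assumptions, not in the documents**
- 1:1 matching.
- k eligible candidates per VIVO patient.
- Normally distributed times with the same SD in both groups.
- The longest candidate is taken in a fraction f of matched sets, and an arbitrary one otherwise.

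**Plausible range of k.** The eligible same-operator share is unknown. At 5%, 10% or 20% of 500 the pool is 25, 50 or 100 cases. Divided by 15, that is 1.7, 3.3 or 6.7 per VIVO patient, before age and gender matching reduces it.

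**Shift in the control mean.** The expected maximum of k standard normal values is E(k) = ∫ x · k · φ(x) · Φ(x)^(k−1) dx, and the shift in SD units is f × E(k).

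| k | E(k): always longest (f = 1) | Longest in a quarter of sets (f = 0.25) |
|---|---|---|
| 1 | 0 | 0 |
| 2 | 0.564 | 0.25 × 0.564 = 0.14 |
| 3 | 0.846 | 0.25 × 0.846 = 0.21 |
| 4 | 1.029 | 0.25 × 1.029 = 0.26 |

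**Effect on a test.** The plan names no test for procedure time against controls. As an illustration, 15 VIVO cases against 15 controls were simulated with no true effect (20,000 runs, unpaired t-test, two-sided 0.05). The chance of a significant result in favour of VIVO was:
- 2.5% when selection ignores procedure time;
- 5.6%, 7.9% and 11.4% with k = 2, 3 and 5 and f = 0.25;
- 21.3% with k = 3 and f = 0.5.

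**For scale.** The 95% confidence half-width for 15 against 15 is t(0.975, 28 df) × √(2/15) = 2.048 × 0.365 = 0.75 SD. The milder shifts lie well inside random error for one study of this size. They are systematic, however, and the confidence interval does not allow for them.

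**The case against.** The strongest reply is that the concern is built on silence. A reader might infer that the selector knows the procedure times, or that the operator will remember and pick the long cases. The documents do not support that: they do not say who selects, which fields the database holds, or what the selector sees. They establish only that the times exist at selection and that no safeguard is described. Nothing suggests that biased selection is intended.

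A reader might also infer that most VIVO patients will have several candidates. The only count is Trust-wide. The low assumption above gives 1.7 per patient before matching, and with one candidate there is no choice and no shift. Nor is 1:1 matching stated; the wording is compatible with using every match, which would remove the discretion. Always taking the longest case would be deliberate cherry-picking, so those figures are upper bounds and not expectations.

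It might further be claimed that the bias could never be found afterwards. That goes too far. The source database exists, nothing says unused records are discarded, and re-extracting all eligible cases could reveal the bias. Analysing only the selected controls could not.

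Finally, section 14 calls the design descriptive and section 14.1 calls it an unpowered feasibility pilot. This limits how much rests on the result and keeps the point at the level of an improvement. It does not answer the point: a biased mean difference is biased with or without a p-value, and section 14.3 still sets a 0.05 threshold, though in its success/recurrence comparison. The statistical team's review in section 13.3 concerns the analysis, not control selection. The eligibility limits in section 6.1 narrow the pool without saying which eligible case is used.

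**Conclusion.** The concern holds as a statement of what the plan permits. Controls for the primary efficacy comparison can be chosen with their procedure times in existence and no rule, lock or masking to prevent those times from influencing the choice. The likely direction is towards a larger apparent saving with VIVO.

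The size cannot be fixed from the documents. Under the stated assumptions it runs from zero (one candidate per patient), through roughly 0.14 to 0.26 SD for an occasional preference among two to four candidates, to upper bounds of 0.56 to 1.03 SD. It rests on 1:1 matching, normal times and the assumed k and f. The documents do not support a claim that biased selection will occur or is intended. This is a cheap improvement, best made before any control is selected.

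**What to change.** Amend sections 6.1 and 14.3 as follows.

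1. Apply the control eligibility criteria to all of the operator's procedures in the five-year window, and state whether one operator or several is meant. Use an extract without procedure time, fluoroscopy time or outcome as far as practicable. Where eligibility needs chart review, record the decision before times are merged.
2. Use every eligible control, stratified or weighted by age and gender. If a fixed ratio is wanted, use a written matching algorithm that gives the age caliper, the ratio and a random or nearest-date tie-break, run by the statistical team mentioned in section 13.3.
3. Lock the control list before procedure times are merged.
4. Report the numbers screened, eligible and used.

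The cost is one restricted extract, a short paragraph of plan text and a small added task for the statistical team, whose stated role is now limited to review. No extra patients are needed. The apparent time saving may turn out smaller.

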4. INTRODUCTION

4.1 BACKGROUND

Accurate localization of the origin of focal ventricular arrhythmias is a prerequisite to successful catheter ablation¹. Nevertheless, mapping and determining the arrhythmic foci is time consuming, invasive and difficult. Catheter ablation guided by VT activation mapping has evolved to treat scar-related arrhythmias with up to 75% success rate after successful mapping procedures. However, non-sustained, non-inducible, or hemodynamically unstable VTs cannot be mapped with this technique. Alternatively, EP substrate mapping during sinus rhythm (SR) identifies the scar EP substrate based on low voltage and the presence of fractionated EGMs and late potentials (LPs). Conventionally, pre-procedural diagnosis and localization of cardiac arrhythmias has been done by the 12 lead ECG ². However, 12-lead ECG arrhythmia-origin algorithms have limitations and may negatively influence ablation outcomes. For example, erroneous identification may result in unnecessary mapping and failure to identify the treatable target ³.

VIVO was developed to easily determine the location of PVC/VT foci and to reduce mapping/identification time. VIVO improves upon the non-invasive 12 lead ECG by combining the ECG data with an already acquired CT/MR image and a 12 lead ECG to create a patient specific model, thus improving the localization accuracy ⁴⁻¹⁰.

4.2 PRE-CLINICAL DATA/CLINICAL DATA

4.2.1 Early Development Study

First in man studies were conducted at the University of California, Los Angeles using the initial VIVO software and algorithm. During the study, the software capabilities and algorithm were fine tuned to improve the accuracy of PVC and VT foci.

The study enrolled 20 patients and had no complications or safety concerns. VIVO correctly identified 100% of the PVC, VT, or stimulation sites to the correct region. Publications from this study are in Attachment A.

4.2.2 Clinical Validation

Previously, 22 patients were enrolled and analysed in a study at Johns Hopkins University Hospital (Baltimore, Maryland) without complications related to VIVO (Satish Misra et al, 2018). Prior to the procedure, imaging (contrast enhanced CT or MRI) was acquired based on the institution's protocol. In addition, a 3D image (to determine ECG lead placement) and ECG data (extracted from CardioLab) were also acquired pre-procedure. Image segmentation, surface electrode registration, and PVC/VT analysis was performed post-procedurally using the VIVO analysis software. VIVO identification of PVCs and VTs was then compared to invasive electro-anatomical mapping (EAM). A PVC location was defined as a site of earliest activation during electroanatomic mapping and/or site of successful ablation. VT was defined as (a) operator defined exit site (b) area of successful ablation.

Results of the study are below:

- 22 patients
- 19/22 locations determined by VIVO were a match to standard mapping systems
- No safety concerns
- Zero complications

A further trial for FDA approval is currently underway with US and European centres contributing.

4.3 STUDY RATIONALE AND RISK/BENEFIT ANALYSIS

4.3.1 Mapping PVC/VT

Outflow tract ventricular tachycardia or frequent premature ventricular tachycardia (PVCs) often occur in the absence of structural heart disease and account for 10% of all ventricular tachycardia (VT). The majority of these originate from the right ventricular outflow tract and the remainder from the left ventricular outflow tract, including cusps of the aortic valve 10. Eighty to 90% of tachycardia in normal hearts originate from the right ventricle, most commonly the right ventricular outflow tract (RVOT)¹¹.

Especially in ischaemic patients, but not only, scar-related re-entry ventricular arrhythmia may involve the endocardium, mid-myocardium, and epicardium. Importantly, the presence of epicardial VT circuits (in about 32% of patients with post-myocardial infarction scars) is considered one of the reasons for failure of a subset of endocardial ablations. Consequently, epicardial mapping via subxyphoidal puncture has evolved as an essential procedure for mapping epicardial scar EP substrate and guiding epicardial ablation, especially in ischaemic cardiomyopathy patients with failed endocardial ablation. Epicardial mapping is associated with procedural complexity and risk of complications. In some cases, catheter access to the epicardium is limited by the presence of pericardial adherence. Non-invasive mapping of epicardial EP substrate and VT activation is therefore a highly desirable procedure. It could aid in deciding whether endocardial or epicardial approach should be used and provide important information for the pre-procedural planning of epicardial ablation. With regards to

endocardial foci, a precise anatomical localization of the “clinical” PVC/VT morphology is critical for the success of the ablation procedure, especially in the setting of hemodynamically poorly tolerated arrhythmias. Over the recent years, the only non-invasive electrocardiographic imaging mapping system validated in the EP laboratory was the CardioInsight (Medtronic, MN, USA), whose accuracy in distinguishing endocardial from epicardial or papillary muscles arrhythmia origin is however limited (margin of error ~6mm). Unlike other existent systems, Vivo™ non-invasive mapping system offers an easier and more accurate localization of PVC/VT foci, allowing to distinguishing endo- from epicardial foci with a high accuracy even with regards to more complex or smaller structures (i.e. anterior from posterior aspect of a papillary muscle, or aortic cusps). The use of such system in a pre-procedural phase can therefore not only increase the success rate of the ablation itself, but also potentially decrease the procedural time (resulting ideally in a reduction of the procedural costs) and radiation exposure time, without adding any risk to the overall procedure.

4.3.2 Procedure Requirements

4.3.2a Prior to EP Procedure

Prior to the procedure the subject will undergo cardiac and thoracic imaging. This can be in the form of a MRI or CT scan, based on physician preference. Specific MRI and CT scan protocols do not significantly differ from the protocols already in use at the Brompton for pre-procedure roadmap scan. The recorded DICOM images should be provided the physician to upload into VIVO for future segmentation. The Mortara 12-lead Holter will be used to record the patient’s PVCs templates (with their respective frequency of presentation). The recorded files will be then imported into Vivo analysis software for the analysis and localization on the pre-reconstructed model. Likewise, the analysis will be done with templates from the Sensis software in the catheter laboratory.

The 3 D Camera will be used to take a 3D image of the patient’s torso after ECG lead placement. This will be merged with the cardiac anatomy from the 3D scan.

4.3.2b During the EP procedure

The EP procedure will be completed per the Institution’s standard of care using a 3D electroanatomical mapping system (CARTO, Biosense Webster).

The information from VIVO analysis will be integrated in the 3D mapping process such that the ablation procedure will be provided with this information, or in post-processing to establish the accuracy of the localization.

Pacing locations can be selected at any time during the procedure based on the physician’s preference.

4.3.2c Registration of EAM to Imaging

Left sided ablations: A Carto mapping catheter will be used to generate a complete fast anatomic map (FAM) anatomic shell of the left ventricle for identification of cardiac structures related to imaging. Imaging should be acquired at End Diastole. Landmarks will include those that are required for the individual procedure, including the papillary muscles if pacing is planned on the papillary muscles.

Right sided ablations: A Carto mapping catheter will be used to generate a complete fast anatomic map of the entire right ventricle and right ventricular outflow tract. Landmarks will include those that are required for the individual procedure.

4.3.2d Identifying the location of PVC or VT Origin

Identification with VIVO: Identifying the location of the PVC or VT foci with VIVO will be done prior to the patient's procedure.

Identification with CARTO: Identifying the location of the PVC or VT foci with Carto can be done at any time during the procedure based on physician preference. Once determined this point should be acquired in CARTO and tagged as Site of Origin. If the Site of Origin cannot be determined by Carto, the "best guess" location will be identified at the discretion of the physician.

4.3.2e Pro-procedure / Post-procedure processing

We will generate a screenshot of each pacing site and the clinical PVC/VT in an orientation that allows adequate visualization of the pacing and arrhythmia locations.

The physician in charge of the analysis will generate a screen shot of the final VIVO analysis for comparison to the Carto screenshots. This will be reviewed with the physician to determine if the VIVO analysis location matches the location identified by Carto.

An electronic copy of the screenshots will be placed in the patient's study file.

